3.4.2. Baseline characteristics

Baseline characteristics (including demographics, disease history and prior anti-cancer therapies) are described in Section 6.5.1. These baseline characteristics are not planned to be included as stratification variables or covariates in statistical models unless otherwise specified in Section 6.

3.5. Safety Endpoints

3.5.1. Adverse events

Treatment-Emergent Adverse Events

Treatment-emergent adverse events (TEAEs) are those events with onset dates occurring during the on-treatment period.

On-treatment period is defined as the time from the first dose of study treatment through minimum (30 days + last dose of study treatment, start day of new anti-cancer drug therapy – 1 day). The start day of new anti-cancer drug therapy after the first dose of study treatment is derived as outlined in Section 5.2.5.

Adverse Events of Special Interest (AESIs)

AESIs are immune-related adverse events (irAE). The criteria for classification of an AE as an irAE are described in Appendix 1.

4. ANALYSIS SETS

Data for all participants will be assessed to determine if participants meet the criteria for inclusion in each analysis population prior to releasing the database and classifications will be documented per Pfizer's standard operating procedures.

Only participants who signed informed consent will be included in the analysis sets below.

Participant Analysis Set	Description
Full analysis set (FAS)	The full analysis set includes all participants who receive at least 1 dose of study drug. Participants will be classified according to the treatment actually received.
Safety analysis set	The safety analysis set includes all participants who receive at least 1 dose of study drug. Participants will be classified according to the study treatment actually received. In this non-randomized study the full analysis set and safety analysis set are identical.
Per-protocol analysis set*	The per-protocol analysis set is a subset of the full analysis set and will not include participants who do not meet criteria that could impact the key objectives of the study*. The per protocol analysis set will be used for sensitivity analyses of the primary efficacy endpoint(s).
DLT-Evaluable analysis set	The DLT-evaluable analysis set includes all participants who receive at least 1 dose of study treatment in Phase 1b and either experience DLT during the DLT-observation period or complete the DLT-observation period without DLT. Participants without DLTs receive less than 75% of the planned dose of each study drug in during the DLT observation period for reasons other than treatment-related toxicity are not evaluable for DLT.
Biomarker analysis set	The biomarker analysis set is a subset of the safety analysis set and includes all participants with at least 1 biomarker evaluated pre-dose.
Pharmacodynamic analysis set	The pharmacodynamic analysis set is a subset of the safety analysis set and includes participants with at least 1 biomarker evaluated pre- and post-dose.
Immunogenicity analysis set	The immunogenicity analysis set is a subset of the safety analysis set and includes participants who have at least 1 analyzed sasanlimab ADA/NAb sample.
PK analysis set	The PK concentration analysis set is a subset of the safety analysis set and will include participants who have at least 1 concentration of any measured analyte related to study drug (i.e., sasanlimab, etc). The PK parameter analysis set is a subset of the safety analysis set and will include participants who have at least 1 of the PK parameters of interest for the measured analytes related to the study drug (i.e., sasanlimab, etc).

*For Sub-Study A criteria: NSCLC with BRAFV600 mutations

*For Sub-Study B criteria: NSCLC with TPS \geq 1%

5. GENERAL METHODOLOGY AND CONVENTIONS

5.1. Hypotheses and Decision Rules

5.1.1. Hypotheses and sample size determination

5.1.1.1. Sub-study A

For Phase 1b, the number of participants to be enrolled in Sub-Study A will depend upon the observed safety profile, which will determine the number of participants at each dose level and the number of dose levels explored. Approximately 9-18 participants will be enrolled in the Phase 1b part for each sub-study.

Beginning with the starting dose level, cohorts of 3-6 participants will be enrolled, treated, and monitored during the 28-day DLT evaluation period (Cycle 1). Participants without DLTs who receive less than 75% of the planned dose of the study intervention in Cycle 1 for reasons other than treatment-related toxicity are not evaluable for DLT. A minimum of 3 DLT-evaluable participants will be required; additional participants will be enrolled in the specific enrollment cohort to replace participants who are not considered DLT-evaluable, where required. When all DLT-evaluable participants treated in a given enrollment cohort have completed the DLT observation period or experienced a DLT, whichever occurs first, the posterior distribution for the risk of DLT for new participants at different dose levels for the combination of interest will be evaluated. The posterior distributions will be summarized to provide the posterior probability that the risk of DLT lies within the intervals shown below:

- Underdosing: $[0, 0.16)$;
- Target toxicity: $[0.16, 0.33)$;
- Excessive toxicity: $[0.33, 1]$.

In addition to accumulating safety data and observed DLTs, decisions on further participant enrollment and dose level selection will be guided by the escalation with overdose control (EWOC) criterion. A combination dose may only be used for newly enrolled participants if the risk of excessive toxicity at that combination dose is less than 25% (0.25). Refer to Appendix 2 for further details of the BLRM.

An RP2D below the MTD, or highest safe dose tested, may be determined based on other safety, clinical activity, PK, and pharmacodynamic data. Before expanding into Phase 2, safety will be confirmed in at least 9 DLT-evaluable participants treated at the RP2D for each combination.

For Phase 2, approximately 62 participants will be enrolled in the Phase 2 part of Sub-Study A.

Phase 2 will test the null hypothesis that the durable ORR does not exceed 35% (H_0 : durable ORR $\leq 35\%$). The null hypothesis will be tested against the alternative (H_1 : durable ORR $> 35\%$) at one-sided level of significance $\alpha = 0.025$ using the binomial distribution.

Sixty-two (62) participants will provide at least 90% power to reject the null hypothesis if the true durable objective response rate is at least 55% (durable ORR $\geq 55\%$).

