A meta-analytic-predictive (MAP) approach was used to derive the prior distribution for the single-agent model parameters. The MAP prior for the logistic model parameters for this study is the conditional distribution of the parameters given the historical data^{1,8,9}. MAP priors are derived using Bayesian hierarchical models, which take into account possible differences between the studies.

A full description of the application of the MAP approach to derive the prior distributions of the single-agent model parameters is given in Appendix 2.

The prior distribution for the interaction parameters (doublet and triplet combinations) were based on the prior understanding of possible drug safety interactions. This prior allows for the possibility of either synergistic or antagonistic interaction, and is fully described in Appendix 2).

It is estimated that up to 18 participants will be enrolled and assigned to treatment with the triplet combination which will include at least 6 participants treated at the MTD level and at least 9 participants at the RP2D. The actual number of participants will depend on the number of DLT events and dose levels tested

Phase 2:

At the end of Phase 2:

- If there are ≤ 29 objective durable responders of 62 participants in the Phase 2 part, then it will be declared that the null hypothesis cannot be rejected.
- If there are ≥ 30 objective durable responders of 62 participants in the Phase 2 part, then the null hypothesis will be rejected.

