6.1.2.1. Sub-Study A - Durable Objective Response

6.1.2.1.1. Primary analysis

Durable ORR is calculated as the proportion of participants in the full analysis population with durable OR along with a 2-sided 95% CI for durable ORR using the Clopper-Pearson method. Participants who do not have a post-baseline tumor assessment due to early progression of disease, who receive anti-cancer therapies other than the study treatments prior to reaching a CR or PR for 10 months, or who die, have PD, or stop tumor assessments for any reason prior to reaching a CR or PR for 10 months will be counted as non-responders in the assessment of Durable OR. Each participant will have a durable objective response status (0: no durable OR; 1: durable OR).

Refer to Section 6.2.2 for assessment of response.

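### Sub-Study A Phase 2: under the plan's own exact rule (reject at 30 or more of 62), power at a 55% durable response rate is 88.0%, not at least 90%

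*SAP*

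**What the plan says.** SAP section 5.1.1.1 sets up the Phase 2 test for Sub-Study A: "Phase 2 will test the null hypothesis that the durable ORR does not exceed 35" per cent, against a one-sided alternative at alpha 0.025, using the binomial distribution. It then claims that "Sixty-two (62) participants will provide at least 90% power to reject the null hypothesis" "if the true durable objective response rate is at least 55" per cent.

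Section 5.1.2.1 turns this into a count. The null is retained "If there are ≤ 29 objective durable responders of 62 participants in the Phase 2 part", and on the other side: "If there are ≥ 30 objective durable responders of 62 participants in the Phase 2 part, then the null hypothesis will be rejected".

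Section 6.1.2.1.1 estimates the durable ORR in the full analysis set with a two-sided 95% Clopper-Pearson interval. Participants who "stop tumor assessments for any reason prior to reaching a CR or PR for 10 months will be counted as non-responders", so they stay in the denominator of 62.

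**The concern.** The null rate, alternative, alpha, sample size and cut-off are all given, so power is fixed and can be recomputed directly. It falls below the stated floor. The wording claims at least 90% at 55%, and 88.0% neither meets nor rounds to that.

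This is the planning figure for the primary endpoint of Sub-Study A Phase 2. A reader who relies on it would take the risk of missing a true 55% rate to be at most 10%, when it is 12.0%, a fifth above the stated maximum. Anyone who recomputes power from the two sections will find the mismatch.

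**Working it through.** **Inputs**

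- Null rate p0 = 0.35, alternative p1 = 0.55, one-sided alpha 0.025, binomial test, n = 62: SAP section 5.1.1.1.
- Reject at 30 or more, do not reject at 29 or fewer: SAP section 5.1.2.1.
- No dropout adjustment: section 6.1.2.1.1 counts participants who stop assessments as non-responders, so n stays 62.

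**Step 1. Trying to reproduce the stated 90%**

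The uncorrected normal approximation, with null variance under the null and alternative variance under the alternative, gives

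n = [(1.96 × √(0.35 × 0.65) + 1.2816 × √(0.55 × 0.45)) / 0.20]² = 61.8, rounded up to 62.

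Its power at n = 62 is Φ{[0.20 × √62 − 1.96 × √(0.35 × 0.65)] / √(0.55 × 0.45)} = 0.901.

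This reproduces both 62 and 90%. Other approximations at n = 62 do not: with continuity correction 0.877, alternative variance only 0.886, arcsine 0.890. The SAP names none of these methods, so the source of the 90% is an inference.

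**Step 2. Exact calculation with the plan's own rule**

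With X ~ Binomial(62, p):

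| Reject at | Type I error, P(reject given 0.35) | Power, P(reject given 0.55) |
|---|---|---|
| 29 or more | 0.0370 | 0.923 |
| **30 or more (plan)** | **0.0205** | **0.8797** |
| 31 or more | 0.0107 | 0.821 |

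The cut-off of 30 is the correct exact critical value, because 29 exceeds alpha 0.025. The Clopper-Pearson lower bound agrees: 35.5% at 30/62 and 34.0% at 29/62. No cut-off at n = 62 gives both alpha at or below 0.025 and power of 90% at 55%.

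Type II error at 55% is 1 − 0.8797 = 0.1203.

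**Step 3. Where 90% is reached**

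Solving P(X ≥ 30 given 62, p) = 0.90 gives p = 0.557.

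**Step 4. Sample sizes that would support 90% at 55%, exact alpha at or below 0.025**

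| n | Reject at | Alpha | Power |
|---|---|---|---|
| 62 | 30 | 0.0205 | 0.880 |
| 64 | 31 | 0.0184 | 0.881 |
| 65 | 31 | 0.0236 | 0.904 |
| 66 | 32 | 0.0165 | 0.882 |
| 67 | 32 | 0.0212 | 0.905 |
| 68 | 33 | 0.0148 | 0.884 |
| 69 | 33 | 0.0190 | 0.906 |

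The smallest is 65. Power drops back below 90% at 66 and 68, then stays at or above 90% from 69 to 74, the largest size checked.

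**Step 5. Effect of the futility look**

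SAP section 7.1 stops for 10 or fewer confirmed responses in the first 30. If the objective response rate were only as high as the durable rate, 55% (a worst-case assumption), the stopping probability is P(X ≤ 10 given 30, 0.55) = 0.0138. That matches the 0.014 in section 7.1. Overall power would then be 0.877. A higher objective response rate would cost less.

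**The case against.** The strongest defence is that the shortfall is small and changes nothing operational. It is about 2 percentage points, and 90% is reached at 55.7% instead of 55%. The hypotheses, cut-off and analysis all stand, and the type I error is controlled. That is right, and it limits the finding to a misstated figure.

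The defence can add that the reference to the binomial distribution describes the test, while the power sentence names no method. One method, the uncorrected normal approximation, could have produced the whole design. It gives 62, power of 90.1% and the same cut-off: z = 1.944 at 29/62, below 1.960, and z = 2.210 at 30/62. So it cannot be asserted that the sample size and the cut-off came from different methods. This stands, but it bears only on where the 90% came from. Whatever formula was used, the rule as written has power 88.0% at 55%. The futility probability in section 7.1 agrees with an exact binomial calculation at 55%, so exact power is the natural expectation here too.

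Finally, loss to follow-up should not be counted as a further reduction. If 55% is the durable ORR as the SAP defines it, participants who stop assessments are already counted as non-responders within that rate. That is correct, and the 88.0% makes no such deduction.

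**Conclusion.** The concern holds. With n = 62 and rejection at 30 or more, exact power at a true durable ORR of 55% is 88.0% against a stated minimum of 90%, and no admissible cut-off at 62 closes the gap. The attained one-sided alpha is 0.0205, so the test and the decision rule remain sound.

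The result uses only the SAP's own inputs. It assumes exactly 62 participants in the full analysis set and no futility stop. The worst-case allowance for futility lowers power only to 87.7%.

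**What to change.** In SAP section 5.1.1.1, and in the protocol if it carries the same claim, replace the power sentence with wording such as: *Using the exact binomial test with rejection at 30 or more of 62 (attained one-sided alpha 0.0205), power is 88% at a true durable ORR of 55%; 90% power is reached at a true rate of about 55.7%.* The sample size, cut-off and analysis stay as they are. The cost is one sentence and a slightly less favourable planning figure.

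If the sponsor prefers to keep the 90% claim, the smallest exact design is 65 participants with rejection at 31 or more (alpha 0.0236, power 0.904). Because section 5.1.1.1 gives enrolment as approximate and power dips again at 66 and 68, a target of 69 or more would be safer, with the cut-off matched to the number actually treated. That route adds participants; the wording correction does not.

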5.1.1.2. Sub-study B

Approximately 20 participants will be enrolled in the Phase 1b dose finding part to evaluate DLTs during the first cycle of treatment in order to confirm the safety of the doublet and triplet combinations and identify the RP2D. However, the total number of participants will depend on the observed safety profile, which will determine the number of participants at each dose level and the number of dose levels explored. Beginning with the first dose level, participants will be enrolled, treated, and monitored in cohorts of 3-4 participants during the 21-day DLT evaluation period (Cycle 1). At least 6 participants will be treated at the RP2D of the triplet combination before proceeding to Phase 2.

Phase 1b will use the mTPI dose finding design with the target toxicity rate of 0.30 with target toxicity interval of (0.25, 0.35).

For Phase 2, approximately 60 participants (20 each in Arms B1, B2 and B3) in total will be enrolled in the Phase 2 part of Sub-Study B.

The primary goal of Phase 2 is to estimate the ORR with standard error ≤ 0.11 . Twenty participants per each treatment arm will provide the specified precision of ORR estimates.

5.1.2. Decision rules

5.1.2.1. Sub-Study A

Phase 1:

The dosing decision and estimation of the MTD of the triplet combination will be guided by the estimation of the probability of DLT in Cycle 1. However, other evidence such as safety data beyond DLT, clinical activity, PK, and PD data will play an important role in the final decision. A RP2D below the MTD may be determined based on these considerations.

Bayesian adaptive approach

The dose finding in the Phase 1b of the study will be guided by a Bayesian analysis of Cycle 1 DLTs in DLT-evaluable participants.⁵

Triplet combination model

For the triplet combination of encorafenib, binimetinib, and sasanlimab, the Bayesian mode⁸ consists of seven parts, representing:

1. Single-agent encorafenib toxicity;
2. Single-agent binimetinib toxicity;
3. Single-agent sasanlimab toxicity;

4. Interaction between encorafenib and binimetinib;
5. Interaction between binimetinib and sasanlimab;
6. Interaction between encorafenib and sasanlimab;
7. Triple interaction among encorafenib, binimetinib, and sasanlimab.

Single-agent toxicities are modelled using logistic regression for the probability of a participant experiencing a DLT against log-dose. The odds of a DLT are then calculated under no interaction for the two/three single-agent toxicities, and interaction is accounted for by adjusting these odds with an additional model parameter (odds multiplier). Details of the model are given in Appendix 2.

Assessment of participant risk

After each dosing cohort of participants completes the DLT evaluation period, the posterior distribution for the risk of DLT for different dose combination doses of interest will be evaluated. The posterior distributions will be summarized to provide the posterior probability that the risk of DLT lies within the following intervals:

- Underdosing: [0, 0.16);
- Target toxicity: [0.16, 0.33);
- Excessive toxicity: [0.33, 1].

The EWOC principle

Dosing decisions are guided by the EWOC principle¹. A combination dose may only be used for the next dosing cohort of participants if the risk of excessive toxicity ([0.33, 1]) at that combination dose is less than 0.25.

Prior distributions

A meta-analytic-predictive (MAP) approach was used to derive the prior distribution for the single-agent model parameters. The MAP prior for the logistic model parameters for this study is the conditional distribution of the parameters given the historical data^{1,8,9}. MAP priors are derived using Bayesian hierarchical models, which take into account possible differences between the studies.

A full description of the application of the MAP approach to derive the prior distributions of the single-agent model parameters is given in Appendix 2.

The prior distribution for the interaction parameters (doublet and triplet combinations) were based on the prior understanding of possible drug safety interactions. This prior allows for the possibility of either synergistic or antagonistic interaction, and is fully described in Appendix 2).

It is estimated that up to 18 participants will be enrolled and assigned to treatment with the triplet combination which will include at least 6 participants treated at the MTD level and at least 9 participants at the RP2D. The actual number of participants will depend on the number of DLT events and dose levels tested

Phase 2:

At the end of Phase 2:

- If there are ≤ 29 objective durable responders of 62 participants in the Phase 2 part, then it will be declared that the null hypothesis cannot be rejected.
- If there are ≥ 30 objective durable responders of 62 participants in the Phase 2 part, then the null hypothesis will be rejected.

5.1.2.2. Sub-Study B

A safe dose will be determined using the adaptive mTPI design. The mTPI design uses a Bayesian statistics framework and a beta/binomial hierarchical model to compute the posterior probability of 3 dosing intervals that reflect the relative difference between the toxicity rate of each dose level to the target probability (pT) rate (pT=0.30). If the toxicity rate of the currently used dose level is far smaller than pT, the mTPI will recommend escalating the dose level; if it is close to pT, the mTPI will recommend continuing at the current dose; if it is far greater than pT, the mTPI will recommend deescalating the dose level. These rules are conceptually similar to those used by the 3+3 design, except the decisions of an mTPI design are based on posterior probabilities calculated under a coherent probability model. As shown by Ji and Wang⁵, mTPI design is more efficient and safer than the 3+3 design. They considered 42 scenarios to cover a wide range of practical dose-response shapes, and concluded that the 3 + 3 design was more likely to treat participants at toxic doses above the MTD and less likely to identify the true MTD than the mTPI design. For example, the 3 + 3 design exhibited a lower overall toxicity percentage than the mTPI design in only 1 of 42 scenarios.

Decision rules are based on calculating unit probability mass (UPM) of 3 dosing intervals corresponding to under, proper, and overdosing in terms of toxicity (Table 8). Specifically, the underdosing interval is defined as $[0, pT-e1]$, the overdosing interval $(pT+e2, 1]$, and the proper-dosing interval $[pT- e1, pT+ e2)$, where e1 and e2 are small fractions. Based on the projected safety profile, e1 is selected as 0.05, and e2 is selected as 0.05. Therefore, the target interval for the DLT rate is $[0.25, 0.35)$. The 3 dosing intervals are associated with 3 different dose-escalation decisions. The underdosing interval corresponds to a dose escalation (E), overdosing corresponds to dose de-escalation (D), and proper dosing corresponds to staying at the current dose (S). Given a dosing interval and a probability distribution, the UPM of that dosing interval is defined as the probability of a participant belonging to that dosing interval divided by the length of the dosing interval. The mTPI design calculates the UPMs for the 3 dosing intervals, and the one with the largest UPM informs the corresponding dose-finding decision, which is the dose level to be used for future participants. For example, if the underdosing interval has the largest UPM, the decision will be to escalate, and the next 3-4 participants will be treated at the next higher dose level. Simulations have demonstrated that

the decision based on UPM is optimal in that it minimizes a posterior expected loss (i.e., minimizes the chance of making a wrong dosing decision).

Table 8. Dose Finding Rules

		Number of Participants Treated at Current Dose															
r\n		3	4	5	6	7	8	9	10	11	12	13	14	15	16	17	18
Number of DLTs	0	E	E	E	E	E	E	E	E	E	E	E	E	E	E	E	E
	1	S	S	S	E	E	E	E	E	E	E	E	E	E	E	E	E
	2	D	S	S	S	S	S	S	S	E	E	E	E	E	E	E	E
	3	DU	DU	D	S	S	S	S	S	S	S	S	S	S	S	E	E
	4		DU	DU	DU	D	D	S	S	S	S	S	S	S	S	S	S
	5			DU	DU	DU	DU	DU	D	S	S	S	S	S	S	S	S
	6				DU	DU	DU	DU	DU	DU	D	S	S	S	S	S	S
	7					DU	DU	DU	DU	DU	DU	DU	D	S	S	S	S
	8						DU	DU	DU	DU	DU	DU	DU	DU	DU	D	S
	9							DU	DU	DU	DU	DU	DU	DU	DU	DU	DU
	10								DU	DU	DU	DU	DU	DU	DU	DU	DU
	11									DU	DU	DU	DU	DU	DU	DU	DU
	12										DU	DU	DU	DU	DU	DU	DU
	13											DU	DU	DU	DU	DU	DU
	14												DU	DU	DU	DU	DU
	15													DU	DU	DU	DU
	16														DU	DU	DU
	17															DU	DU
18																DU	

E = Escalate to the next higher dose level
 S = Stay at the current dose level
 D = De-escalate to the next lower dose level
 DU = The current dose level is unacceptably toxic and should be eliminated from further dose finding
 DLTs = Dose Limiting Toxicities; Targeted DLT rate=30%

Select escalation/de-escalation algorithms for total number of participants treated at the current dose level (current and previous cohorts):

For example based on Table 8, with 6 participants treated at current dose level

- 0-1 DLT: escalate
- 2-3 DLTs: remain at the same dose
- 4-6 DLTs: de-escalate and consider current dose as intolerable

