A minimum of 3 DLT-evaluable participants will be required in each cohort; additional participants will be enrolled in the specific enrollment cohort to replace participants who are not considered DLT-evaluable, where required. When all DLT-evaluable participants treated in a given enrollment cohort have completed the DLT observation period or experienced a DLT, whichever occurs first, the posterior probabilities for the risk of DLT for new participants at different dose levels for the combination of interest will be evaluated. If the toxicity rate of the currently used dose level is far smaller than the target probability of toxicity (pT) of 0.30, the mTPI will recommend escalating the dose level; if it is close to pT, the mTPI will recommend continuing at the current dose; if it is far greater than pT, the mTPI will recommend de-escalating the dose level. The mTPI dose de-escalation/escalation recommendation will be based on the estimated toxicity rate and 3 intervals (underdosing, target toxicity, and excessive toxicity) as shown below:

- If current dose is in the underdosing [0, 0.25) toxicity interval: escalate to next higher dose;
- If current dose is in the target toxicity [0.25, 0.35) toxicity interval: stay at current dose;
- If current dose is in the excessive toxicity or overdosing [0.35, 1] toxicity interval: de-escalate to a lower dose

The number of participants to be enrolled in Phase 1b will depend upon the observed safety profile, which will determine the number of participants at each dose level and the number of dose levels explored.

It is anticipated that up to approximately 20 total participants will be enrolled in Phase 1b starting with Dose Level 0 of the doublet cohorts and including the triplet cohorts.

An RP2D below the MTD, or highest safe dose tested, may be determined based on other safety, clinical activity, PK, and pharmacodynamic data.

Cumulative DLT data will continue to be evaluated using the mTPI design in the Phase 2 part. Should emerging data indicate that the dose level tested in the Phase 2 expansion cohort is more toxic than previously estimated ($\geq 35\%$ DLT rate), the next lower dose level may be explored, and may be declared as the RP2D for the triplet combination.

Phase 2 Design:

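### One cell of the Sub-Study B mTPI table (3 DLTs among 16 participants) prints S where the largest-UPM rule gives E

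*SAP*

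**What the plan says.** SAP section 5.1.2.2 (Sub-Study B) describes an mTPI design that uses "a beta/binomial hierarchical model to compute the posterior probability of 3 dosing intervals". The target toxicity rate is 0.30 and "e1 is selected as 0.05, and e2 is selected as 0.05", so the target interval for the DLT rate is 0.25 to 0.35. The UPM of an interval is "the probability of a participant belonging to that dosing interval divided by the length of the dosing interval". Of the three intervals, "the one with the largest UPM informs the corresponding dose-finding decision". Underdosing leads to escalation (E), the target interval to staying (S), and overdosing to de-escalation (D). A fourth code, DU, eliminates a dose as unacceptably toxic.

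Table 8 lists the decision for each number of DLTs and each number treated from 3 to 18. Its row for 3 DLTs reads DU at n = 3 and 4, D at n = 5, S from n = 6 to n = 16, and E at n = 17 and 18.

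On scale, section 2.2.2 says: "It is anticipated that up to approximately 20 total participants will be enrolled in Phase 1b". That section also continues mTPI evaluation of cumulative DLTs in Phase 2. If the DLT rate there proves to be 35% or more, "the next lower dose level may be explored, and may be declared as the RP2D for the triplet combination".

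**The concern.** Table 8 is the operative form of the rule, since it is what a dosing decision would be read from. If a cell differs from the rule, someone who programs the rule and someone who reads the table reach different recommendations from the same data. In the row for 3 DLTs, the change from S to E appears one column later than the rule puts it. Nothing in section 5.1.2.2 marks the cell as an intended departure.

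**Working it through.** **Inputs from SAP section 5.1.2.2.** Target rate 0.30; e1 = e2 = 0.05; beta/binomial model; UPM = interval probability / interval length; the largest UPM decides.

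**Inputs not stated in the SAP.** The beta prior and the DU cut-off. I assume Beta(1,1) and DU when Pr(p > 0.30 | data) > 0.95, and test both choices below. The cut-off has no bearing on the cell in question, where Pr(p > 0.30) is 0.202.

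**Formulas.** With r DLTs among n participants the posterior is Beta(1 + r, 1 + n − r), with distribution function F.

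- UPM(under) = F(0.25) / 0.25
- UPM(target) = [F(0.35) − F(0.25)] / 0.10
- UPM(over) = [1 − F(0.35)] / 0.65

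**Reproducing the table.** Columns n = 3 to 18 with r = 0 to n give 4 + 5 + … + 19 = 184 filled cells. Of these, 183 match, including every DU cell. The one mismatch is r = 3, n = 16.

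**The cell itself.** The posterior is Beta(4, 14), with F(0.25) = 0.6470 and F(0.35) = 0.8972.

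- Under: 0.6470 / 0.25 = 2.588
- Target: (0.8972 − 0.6470) / 0.10 = 2.502
- Over: (1 − 0.8972) / 0.65 = 0.158

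Underdosing is largest, so the rule gives E. Table 8 prints S.

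**Neighbouring and closer cells.**

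| DLTs / n | UPM under | UPM target | UPM over | Lead of largest | Rule | Table 8 |
|---|---|---|---|---|---|---|
| 3/15 | 2.380 | 2.711 | 0.206 | 13.9% | S | S |
| **3/16** | **2.588** | **2.502** | **0.158** | **3.4%** | **E** | **S** |
| 3/17 | 2.777 | 2.274 | 0.120 | 22.1% | E | E |
| 2/11 | 2.437 | 2.394 | 0.233 | 1.8% | E | E |
| 7/15 | 0.109 | 1.323 | 1.293 | 2.3% | S | S |

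Two cells are closer than 3/16 and both are printed as the rule requires. One of them, 2/11, is the same contest between underdosing and target. Rounding, or a tie-break towards caution, therefore does not explain 3/16.

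**Could another prior explain it?**

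- Beta(0.5, 0.5) gives E at 3/16 and mismatches 7 cells in all.
- Beta(2, 2) gives S at 3/16 but breaks 14 other cells.
- On a grid of 1,849 priors (both parameters from 0.40 to 2.50 in steps of 0.05, cut-off 0.95), none reproduces all 184 cells. Thirteen leave a single mismatch, and it is always 3/16. Every prior on the grid that turns 3/16 into S breaks at least two other cells.

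**Could another cut-off or other margins explain it?** Under Beta(1,1), a cut-off between 0.94999 (7/14, printed D) and 0.95265 (5/9, printed DU) is needed to reproduce the DU cells, which supports 0.95. With e1 and e2 varied from 0.03 to 0.07 in steps of 0.005, no pair reproduces the whole table. Where 3/16 does become S, other cells fail, such as 2/11.

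**Could text extraction explain it?** The row for 3 DLTs has 16 entries for 16 columns, and the other 15 match, so no entry was dropped or shifted.

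**The case against.** The case against rests on materiality. With about 20 participants across doublet and triplet cohorts and at least 6 required at the triplet RP2D, 16 at one doublet level would leave about 4. Sixteen at one triplet level plus 3 or 4 in the doublet makes 19 or 20, leaving no room for another cohort of 3. At the top dose level E and S coincide anyway. In Phase 2 the only action described is de-escalation at a DLT rate of 35% or more, and 3/16 = 18.75%, so E and S lead to the same described result. The printed S exposes nobody to a higher dose, and mTPI is described as guiding decisions rather than dictating them. Finally, the rule cannot be computed as written because no prior is given, so the mismatch is with a reconstructed rule.

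Most of this stands as a limit on importance. It does not remove the discrepancy. The figure of 20 is approximate and depends on observed safety, so the cell is unlikely to be reached but not impossible. The table runs to n = 18. The reconstruction is an inference, but 183 matching cells support it, and no prior on the grid rescues the odd one. General discretion over dosing does not account for one unannotated entry in a table presented as the output of the rule.

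**Conclusion.** The cell for 3 DLTs among 16 participants is inconsistent with the largest-UPM rule: it prints S where the rule gives E. It is 1 of 184 cells, and the underdosing UPM leads by about 3%. The conclusion rests on a Beta(1,1) prior, which the SAP does not state but which the rest of the table supports. The entry is either an isolated slip or an undocumented exception. The error is in the cautious direction, changes no estimate or error rate, and is unlikely to affect any dosing decision. It is a minor correction.

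**What to change.** In Table 8, change the entry for 3 DLTs and n = 16 from S to E. If S is intended, add a footnote saying that this cell is a deliberate conservative exception to the largest-UPM rule. The choice is the sponsor's, and the cost is one table cell or one footnote. Nothing else in the design needs to change.
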